Twenty-four eligible participants will be block-randomized 1 to 1 treatment (12 participants) and control (12 participants) groups. All participants will undergo endoscopy and those without endoscopic contraindications will be eligible. All treatment group subjects will undergo combined HAPC and ESG where APC is applied according to on-label use prior to the standard ESG technique for enhanced fibrosis along the site of the plications potentially providing an avenue for longer and more durable ESG while minimizing the associated complications. Control subjects will undergo traditional ESG alone. All participants will undergo a repeat upper endoscopy at 26 weeks (6 months) +/- 2 weeks to evaluate the durability of the endoscopic sutures. All subjects will undergo research MRI at baseline and 26 weeks +/- 2 weeks to evaluate and grade the durability of the created gastroplasty, gastric motility, and gastric accommodation. This specially developed MRI protocol at Mayo offers a gold standard in evaluating gastroplasty durability. Additionally, at both baseline and 26 weeks +/- 2 weeks, all patients will undergo gastric scintigraphy to evaluate and measure gastric emptying.

Endpoints Effectiveness

Primary:

- Assess durability of endoscopic plications and sutures 26 weeks (6 months) +/- 2 weeks post procedure between patients receiving HAPC/ ESG vs traditional ESG alone.

Secondary:

- %TBWL in the combined HAPC and ESG group compared to traditional ESG at 6 and 12 months.
- Assess the procedure safety.
- % Excess weight loss (EWL) at 6 and 12 months between both groups.
- Proportion with $\geq 25\%$ EWL at 6 and 12 months by randomized arm.
- % of patients in the combined HAPC and ESG group achieving $\geq 5\%$ TBWL at 6 and 12 months compared to ESG alone.
- % of patients in the combined HAPC and ESG group achieving $\geq 10\%$ TBWL at 6 and 12 months compared to ESG alone.
- Changes in quality of life assessed using standard validated questionnaires (IWQOL-lite and SF-36) at 6 and 12 months compared to baseline.
- Changes in depression assessed using PHQ-9 questionnaire at 6 and 12 months compared to baseline.

- Improvement/reduction of hunger and desire to eat evaluated using validated self-reported ratings of appetite based on a 100-mm visual-analogue scale at 6 and 12 months compared to baseline.
- Improvement in eating behaviors evaluated using the Three Factor Eating Questionnaire (TFEQ) at 6 and 12 months compared to baseline.

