Patients withdrawn prior to undergoing combined HAPC and ESG or ESG alone will count towards the target accrual. Screen failed patients will not count towards target accrual. New patients will be randomized to target accrual of 24 total patients receiving combined HAPC and ESG or ESG alone. The power and sample size calculation includes sufficient patients to yield power assuming some post-intervention dropout.

Source Documentation

Study source worksheets and/or electronic documentation in the medical record will be used as source documentation for the trial for all participant follow-up visits. Source documentation from the electronic medical record will be required for the procedure(s), medications, and any serious adverse medical events. REDCap will be used for collection of electronic sources and verified by PI attestation as the eCRF. If unavailable to conduct electronic source, physical CRF source worksheets will be available and can be added to the eCRF for investigator attestation.

PROTOCOLS FOR PROCEDURE AND IMAGING

HybridAPC (HAPC) Application

HAPC will be performed in conjunction with ESG in patients in the treatment group. The location is from the level of the incisura all the way to the fundus. The pattern includes 3 rectangular APC ablation zones created on the anterior, greater curvature and posterior surface of the stomach. The HAPC is composed of a submucosal lift followed by ablation. The default setting of the APC is 50 Watts, 1 L/min flow, but it may be adjusted within normal clinical limits dependent on participant anatomy and tissue response. After ablation, ESG will be performed in standard fashion.

Measurement of Gastric Accommodation by Dynamic MRI

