The primary endpoint for power and sample size is durability of plications on repeat endoscopy 6 months after initial procedure with HAPC and ESG and ESG alone. Another primary endpoint for power and sample size is %TBWL at 6 and 12 months.

We plan a 1:1 randomization scheme that allocates to either HAPC ESG (12 patients) or ESG alone (12 patients). Given the pilot nature of this trial, no formal power calculation is feasible or warranted.

Statistical Analysis

Statistical analyses of randomized groups at 6 and 12 months will be performed based on a modified intent-to-treat (mITT) principle for efficacy analyses. Patients randomized but subsequently withdrawn or identified as meeting exclusion criteria prior to intervention (as applied to both the treatment and control arms) will be excluded from the analysis if the reason for exclusion is documented and unrelated to the randomized arm.

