8.2.1 Primary Aim

The primary outcomes are durability of plications and endoscopic sutures on repeat endoscopy at 6 months, in the two randomized arms.

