8.2.2 Secondary Aims

Continuous secondary outcomes, including %TBWL^b, %EWL^c, change in systolic and diastolic blood pressure and change in HbA1c, QOL questionnaires such as the SF-36, IWQOL, PHQ-9, and eating behavior scores will be compared between treatment arms using ANCOVA with adjustment for the same variables specified in the primary analysis.

Binary outcomes, including proportion with $\geq 25\%$ reduction in %EWL and incidence of esophagitis will be compared between treatment arms by Pearson Chi-square test.

Among all subjects, %EWL will be compared at 6 and 12 months between both arms of the study.

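### Three internal contradictions need reconciling: whether %TBWL is primary or secondary, a power claim with no calculation behind it, and two replacement rules that cannot both be followed

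*Combined protocol and SAP*

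**What the plan says.** **Endpoint status.** Power and Sample Size first names durability of the plications at 6 months as the primary endpoint, then adds: "Another primary endpoint for power and sample size is %TBWL at 6 and 12 months". The list under Endpoints Effectiveness puts durability alone under Primary and has, as its first Secondary item, "TBWL in the combined HAPC and ESG group compared to traditional ESG at 6 and 12 months". Section 8.2.1 reads "The primary outcomes are durability of plications and endoscopic sutures on repeat endoscopy at 6 months" and does not mention weight. Section 8.2.2 opens with "Continuous secondary outcomes, including %TBWL".

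**Power.** Power and Sample Size says: "Given the pilot nature of this trial, no formal power calculation is feasible or warranted". Replacement of withdrawn subjects says: "The power and sample size calculation includes sufficient patients to yield power assuming some post-intervention dropout".

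**Accrual.** The replacement section says "Patients withdrawn prior to undergoing combined HAPC and ESG or ESG alone will count towards the target accrual". Two sentences later it says "New patients will be randomized to target accrual of 24 total patients receiving combined HAPC and ESG or ESG alone". Between them it says that screen failures do not count. General Description randomizes 24 patients, 12 per arm, and Study Setting limits maximum enrolment to 24.

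**The concern.** Each pair of statements gives two answers to a question that should have one before results are known.

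- The sentence on %TBWL gives an author a textual basis for reporting weight loss at either time point as a primary result, although three sections make it secondary and no multiplicity rule is given.
- The replacement section credits the trial with power, even after dropout, that no calculation in the documents supports.
- The two accrual sentences matter for conduct. The first patient who withdraws between randomization and procedure leaves staff with one instruction to count that patient and another to randomize a replacement. The modified intent-to-treat set is built on patients who received the intervention (8.2.3), so the choice changes the number analysed.

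**Working it through.** **1. Endpoint status, side by side**

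| Section | Durability at 6 months | %TBWL at 6 and 12 months |
|---|---|---|
| Endpoints Effectiveness | primary | secondary |
| Power and Sample Size | primary, for sizing | another primary, for sizing |
| 8.2.1 | primary | not mentioned |
| 8.2.2 | not mentioned | secondary |

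Three sections agree and one differs. The one that differs ties the label to power and sample size, but then says no power calculation applies. Nothing was sized on %TBWL, so the label does no work there.

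**2. The sample size**

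The only figure that can be reproduced is 12 + 12 = 24. It agrees across General Description, Study Setting and Power and Sample Size. No alpha, sidedness, power, effect size, standard deviation, event rate, dropout rate or required evaluable number is stated, so the claim to yield power after dropout cannot be checked. The Missing Data section keeps patients with at least one follow-up visit in the model under a missing-at-random assumption. That is an analysis rule and does not supply a power allowance.

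**3. The two accrual rules**

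Let w be the number of patients who withdraw after randomization and before the procedure.

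- If withdrawals count towards a target of 24, 24 are randomized and 24 − w are treated.
- If randomization continues until 24 are treated, 24 + w are randomized.

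The rules agree only when w = 0. With w = 1 they give 23 treated or 25 randomized.

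**4. How likely is w > 0?**

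The documents give no pre-procedure loss rate. Assume a rate q per patient, independent between patients:

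| Assumed q | Chance of at least one loss among 24: 1 − (1 − q)^24 | Average treated if 24 are randomized: 24(1 − q) | Average randomized to treat 24: 24/(1 − q) |
|---|---|---|---|
| 2% | 1 − 0.616 = 38% | 23.5 | 24.5 |
| 5% | 1 − 0.292 = 71% | 22.8 | 25.3 |
| 10% | 1 − 0.080 = 92% | 21.6 | 26.7 |

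The plan itself foresees such losses: Statistical Analysis and Missing Data both provide for patients who withdraw or are excluded between randomization and intervention. The procedure may follow randomization by up to 60 days (Trial Intervention).

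**5. The cap of 24**

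If enrolment in Study Setting means randomized, as General Description suggests, the first replacement exceeds the cap. If it means treated, the cap fits the replacement sentence, and the conflict is confined to the two sentences in the replacement section.

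**The case against.** **The %TBWL label is minor.** It is limited to power and sample size, and the endpoint list and both analysis sections are clear. This stands: on its own, part 1 is a small wording error. A reader might go further and infer that the trial has three primary tests with inflated type I error. Three independent unadjusted tests at an assumed 0.05 would give 1 − 0.95³ = 14.3%. The documents do not support treating this as the trial's error rate. They state no alpha, and the three-test family exists only if %TBWL is primary, which three sections contradict.

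**A pilot needs no power calculation.** Agreed, and its absence is not the point. The fault is that another section claims its result. A reader might also infer that no dropout allowance was ever considered. The documents show only that none is stated; the sponsor alone can say whether one was made.

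**The cap may not be breached.** A reader might infer that the replacement rule flatly breaks the cap of 24. Study Setting does not define enrolment, so that holds only if enrolment means randomized. The conflict inside the replacement section holds on either reading.

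**Endoscopic contraindications may be screen failures.** The endoscopy that rules out contraindications takes place at the procedure visit (Trial Intervention; Schedule of Events), after randomization. It is tempting to cite these as certain pre-procedure withdrawals. But General Description makes absence of endoscopic contraindications a condition of eligibility, and screen failures do not count towards accrual. The documents do not say which class such a patient falls in. Other withdrawals before the procedure remain possible, so the conflict does not depend on this.

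**Conclusion.** The point holds as three internal inconsistencies. The %TBWL label is the least serious. The power sentence is unsupported as written. The accrual conflict has the most practical effect, because a single pre-procedure withdrawal makes the two rules incompatible.

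That conflict follows from the text and needs no assumption. Only its likelihood does: 38% to 92% for at least one loss among 24, at assumed loss rates of 2% to 10% that are not document figures. None of the three parts calls the size of 24, the 1:1 allocation or the choice of endpoints into question.

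**What to change.** 1. **Power and Sample Size.** Delete the sentence that calls %TBWL another primary endpoint, or change it to read secondary endpoint. Report %TBWL as secondary.

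2. **Replacement of withdrawn subjects, power sentence.** Replace it with: *The sample size of 24 reflects the pilot nature of the trial; no formal power calculation was done and no power is claimed.* The sponsor should state any dropout allowance that was made, or remove the reference to one.

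3. **Accrual.** Give 24 one meaning in General Description, Study Setting and the replacement section.
   - *If 24 means treated:* delete the sentence that counts pre-procedure withdrawals towards accrual; otherwise the contradiction remains. Reword General Description and the cap as 24 treated, and give a separate ceiling for patients randomized. At 2% to 10% loss, the averages above round up to 25 to 27. State whether a contraindication found at the procedure endoscopy is a screen failure or a withdrawal.
   - *If 24 means randomized:* delete the sentence that randomizes new patients, and say that fewer than 24 may be treated (about 21.6 to 23.5 on average at the same loss rates).

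**Cost.** Items 1 and 2 are sentence edits that change no visit, test or patient; the trial gives up only a power statement it cannot support. Item 3 is a choice of wording whose price is either about one to three more patients randomized or a slightly smaller treated group.

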8.2.1 Primary Aim

The primary outcomes are durability of plications and endoscopic sutures on repeat endoscopy at 6 months, in the two randomized arms.

8.2.2 Secondary Aims

Continuous secondary outcomes, including %TBWL^b, %EWL^c, change in systolic and diastolic blood pressure and change in HbA1c, QOL questionnaires such as the SF-36, IWQOL, PHQ-9, and eating behavior scores will be compared between treatment arms using ANCOVA with adjustment for the same variables specified in the primary analysis.

Binary outcomes, including proportion with $\geq 25\%$ reduction in %EWL and incidence of esophagitis will be compared between treatment arms by Pearson Chi-square test.

Among all subjects, %EWL will be compared at 6 and 12 months between both arms of the study.

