- Improvement in obesity related comorbidities (blood pressure, fasting glucose, HbA1c, lipid panel, liver enzymes) at 6 and 12 months compared to baseline.
- Changes in gastric motility, volume, accommodation, and constructed gastroplasty on MRI at 6 months compared to baseline.
- Changes in gastric emptying evaluated by gastric emptying study at 6 months compared to baseline.
- Changes in liver biochemical panel, and glucose homeostasis parameters at 6 months compared to baseline between the two groups.

Safety

- The incidence, frequency, and severity of adverse events related to treatment with the device will be reported throughout the duration of the study.
- Goal is <5% rate of serious adverse events related to the device or procedure (as determined by the site PI). Serious adverse events will be classified in the Adverse Events table.

Study Setting

The study will be conducted at 1 US center, Mayo Clinic in Rochester, MN. The maximum enrollment will be limited to 24 participants. The expected enrollment period is 6 months.

Subjects

Participants will be adult patients (Ages 21 \geq and \leq 65) with a BMI \geq 30 and \leq 40 kg/m² that meet the eligibility criteria below. All eligibility criteria must be met at the time of randomization.

Inclusion Criteria

1. Age 21-65
2. BMI \geq 30 and \leq 40 kg/m²
3. Willingness to comply with the substantial lifelong dietary restrictions required by the procedure.
4. History of failure with non-surgical weight-loss methods.
5. Willingness to follow protocol requirements, including signed informed consent, routine follow-up schedule, completing laboratory tests, and completing diet counseling.

6. Residing within a reasonable distance from the investigator's office and able to travel to the investigator to complete all routine follow-up visits.
7. Ability to give informed consent.
8. Women of childbearing potential (i.e., not post-menopausal or surgically sterilized) must agree to use adequate birth control methods.

Exclusion Criteria

1. History of foregut or gastrointestinal (GI) surgery (except uncomplicated cholecystectomy or appendectomy).
2. Prior gastrointestinal surgery with sequelae, i.e. obstruction, and/or adhesive peritonitis or known abdominal adhesions.
3. Prior open or laparoscopic bariatric surgery.
4. Prior surgery of any kind on the esophagus, stomach, or any type of hiatal hernia surgery.

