8.2.3 Secondary Analyses

A per-protocol analysis will compare randomized groups among protocol adherent patients – here, defined among as those actually receiving the procedure and making $\geq 80\%$ follow-up visit in both groups. Modified ITT will be considered the primary approach for all efficacy analyses and will include patients who actually received the intervention regardless of adherence to follow-up visits. Safety endpoints and adverse events may be evaluated based on treated group (per-protocol).

Additional outcomes and analyses not specified here are considered exploratory and post-hoc and will be clearly identified as such in any publications.

^b %TBWL defined as $[(\text{pre-operative weight} - \text{post-operative weight}) / (\text{pre-operative weight})] \times 100$

^c % EWL defined as $[(\text{pre-op weight} - \text{follow up weight}) / (\text{pre-op weight} - \text{ideal body weight})] \times 100$

Note: "Ideal body weight" of BMI 25

Missing Data

The primary analysis uses a hierarchical regression model, assuming post-randomization dropout is missing at random (MAR) among subjects completing at least 1 of the planned follow up visits.

Patients excluded after randomization and before intervention on the basis of identified exclusion criteria will be excluded from analyses; reasons for meeting exclusion criteria will be documented. Patients that withdraw/dropout between randomization and intervention are assumed to be missing completely at random. However, a sensitivity analysis will compare withdrawn subjects to participating subjects and perform analyses under MAR (including multiple imputation) assumptions if these subjects appear different or if dropout occurs at substantially different rate in one arm compared to the other. Participating patients who dropout prior to the first follow up visit will be analyzed similarly.

Randomization and Data Collection

Stratified block randomization schedules will be uploaded to REDCap. Data will be collected in REDCap data collection forms.

Interim Analysis

No interim analysis will be performed for efficacy endpoints. Adverse events will be monitored throughout and discussed with the data monitoring committee.

ETHICAL CONSIDERATIONS

This study is to be conducted according to United States government regulations and Institutional research policies and procedures.

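### The ANCOVA for continuous secondary outcomes takes its covariates from a primary analysis that names none, so adjustment for each outcome's own baseline is not provided for

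*Combined protocol and SAP*

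**What the plan says.** Section 8.2.2 gives one covariate rule for all continuous secondary outcomes. They "will be compared between treatment arms using ANCOVA with adjustment for the same variables specified in the primary analysis". The outcomes it lists include %TBWL, %EWL, "change in systolic and diastolic blood pressure and change in HbA1c", the quality-of-life questionnaires, PHQ-9 and eating-behaviour scores.

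The section it points back to, 8.2.1, reads: "The primary outcomes are durability of plications and endoscopic sutures on repeat endoscopy at 6 months, in the two randomized arms". It names no model, test or adjustment variable. Two other places touch on the primary model or on possible covariates, and neither names a variable:

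- Missing Data: "The primary analysis uses a hierarchical regression model, assuming post-randomization dropout is missing at random (MAR".
- Randomization and Data Collection: "Stratified block randomization schedules will be uploaded to REDCap". No strata are given, and the Randomization section describes variable blocks without mentioning strata.

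The effectiveness endpoint list frames the clinical and physiological outcomes against baseline. For the questionnaires it gives "Changes in quality of life assessed using standard validated questionnaires (IWQOL-lite and SF-36) at 6 and 12 months compared to baseline", and it treats PHQ-9 in the same way. For gastric physiology an example is "Changes in gastric emptying evaluated by gastric emptying study at 6 months compared to baseline". The Screening & Enrollment list obtains vital signs, laboratory tests, questionnaires, MRI and gastric emptying at baseline, and HbA1c is in the laboratory panel.

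**The concern.** A covariate list shared across outcomes has to make sense for all of them. Durability has no pre-procedure value, so a list written for it would not naturally contain baseline systolic pressure, HbA1c or a PHQ-9 score. If the rule is followed literally with the list as it stands, which is empty, the blood pressure and HbA1c analyses become plain change-score comparisons labelled ANCOVA.

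Two things are at stake. One is precision: an unadjusted change score has a larger variance than the baseline-adjusted comparison unless the correlation is very high. The other is chance imbalance. With 12 per arm the groups will often differ at baseline, and an unadjusted change score carries part of that difference into the estimated treatment effect through regression to the mean. These outcomes support the stated objective on obesity-related comorbidities.

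**Working it through.** **Inputs from the documents.** 12 per arm, 1:1 (Power and Sample Size). The same section declines a formal power calculation, so there is no figure of the plan's own to reproduce.

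**Assumed inputs, not in the documents.** Two-sided alpha 0.05; follow-up SD = 1 and equal to the baseline SD; true difference d of 0.3 to 1.0 SD; baseline-to-follow-up correlation rho of 0.3 to 0.9; no dropout.

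**Formulas.**

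- Change score, unadjusted: variance 2(1 − rho), 22 df.
- ANCOVA on own baseline: variance (1 − rho²) × (1 + 1/20), 21 df. The factor 1.05 allows for estimating the slope.
- Noncentrality: d / sqrt(variance × 2/12). Power comes from the noncentral t distribution.

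**Variance ratio, ANCOVA to change score.** (1 − rho²) / [2(1 − rho)] = (1 + rho)/2. This is 0.65, 0.75, 0.85 and 0.95 at rho 0.3, 0.5, 0.7 and 0.9. Multiplied by 1.05 it becomes 0.68, 0.79, 0.89 and 1.00, so nothing is gained at rho 0.9.

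**Worked case, rho 0.5 and d = 1.0.**

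- Change score: variance 1.0, standard error sqrt(1.0 × 2/12) = 0.408, noncentrality 2.449, power 0.649.
- ANCOVA: variance 0.75 × 1.05 = 0.7875, standard error sqrt(0.7875 × 2/12) = 0.362, noncentrality 2.760, power 0.749.
- Gain: 10 points.

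**Range (power, change score → ANCOVA).**

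| Effect | rho 0.3 | rho 0.5 | rho 0.7 | rho 0.9 |
|---|---|---|---|---|
| 0.3 SD | 0.091 → 0.111 | 0.108 → 0.124 | 0.148 → 0.160 | 0.349 → 0.349 |
| 0.5 SD | 0.168 → 0.223 | 0.216 → 0.261 | 0.327 → 0.359 | 0.745 → 0.744 |
| 0.8 SD | 0.354 → 0.481 | 0.466 → 0.558 | 0.677 → 0.724 | 0.987 → 0.987 |
| 1.0 SD | 0.508 → 0.666 | 0.649 → 0.749 | 0.856 → 0.891 | 0.999 → 0.999 |

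The gain runs from nil to 16 points. At 10 per arm, rho 0.5 and 0.8 SD, it is 8 points (0.395 → 0.472).

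**Chance imbalance.** The SD of the baseline difference between arms is sqrt(2/12) = 0.408, so P(|difference| > 0.5 SD) = P(|Z| > 1.22) = 0.22 for any one outcome. Given a 0.5 SD imbalance, the unadjusted change-score estimate is shifted by (1 − rho) × 0.5 SD: 0.35, 0.25 and 0.15 SD at rho 0.3, 0.5 and 0.7.

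**The case against.** A reader might infer that the plan definitely leaves baselines out of these models. The documents do not support that. There is no covariate list to borrow, so nothing is shown to be excluded; the adjustment is simply not provided for. The word ANCOVA, applied to change outcomes, even suggests that baseline adjustment may have been intended.

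Nor is it certain which primary analysis is meant. Power and Sample Size calls %TBWL another primary endpoint, and a hierarchical model among patients with at least one follow-up visit suits a repeatedly measured weight better than a single week-26 endoscopy. This stands as a caution, but it does not remove the point: a weight-based list might hold baseline weight or BMI, but it would still not naturally hold baseline HbA1c, blood pressure or PHQ-9. A primary-analysis text that named the baseline value of the outcome where one exists would make the cross-reference work, but no such text is there.

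A reader might also infer a fixed loss of about 10 points of power. That figure holds only near rho 0.5 with an effect of 0.8 to 1.0 SD, and the documents give neither quantity.

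Finally, these are secondary outcomes in a 24-patient pilot without a power target. Under randomisation an unadjusted change score is unbiased on average. That is correct, and it limits the cost to precision and to chance imbalance in the trial actually run.

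**Conclusion.** The point holds as a gap in specification with a clear better choice. The covariates of the secondary ANCOVA are defined only by a reference that leads to no variables, and nothing commits any model to its outcome's own baseline, although those values are collected. The benefit of own-baseline adjustment over an unadjusted change score is about 0 to 16 points of power under the assumed ranges. It is smallest where the effect is small or the correlation high. Added to this is protection against a baseline difference of more than 0.5 SD, which chance alone produces in about 22% of such trials for any one outcome. All of these sizes rest on assumed effects and correlations. This is a free improvement and not a threat to the trial's validity.

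**What to change.** In section 8.2.2, replace the reference to the primary analysis with wording such as:

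> with adjustment for the baseline value of that outcome where one exists (for %TBWL and %EWL, which are already changes from pre-operative weight, baseline weight or BMI), plus any factor actually used to stratify randomisation.

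The clause on %TBWL and %EWL is needed because footnotes b and c define both as relative to pre-operative weight, so neither has a baseline value of its own. Apply the same rule to the other laboratory outcomes (fasting glucose, lipids, liver enzymes), to gastric emptying, and to MRI volume, accommodation and motility. At this sample size, add no further covariates.

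The cost is one sentence and one residual degree of freedom per model for the baseline term, already counted in the power figures above. Any stratification term would use its own degrees of freedom. No new data are needed.

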ESG is a commonly performed procedure that has been shown to demonstrate significant weight loss. However, combining it with HAPC technique to enable approximation of submucosal surfaces for enhanced gastroplasty healing, durability of this procedure could be enhanced. This could help maximize the metabolic benefits of gastric mucosal revitalization in conjunction with the restrictive effects of ESG for enhanced weight loss, durability, and metabolic benefits of the combined procedure while minimizing the risk of weight recurrence previously reported with the traditional ESG.

STUDY OBJECTIVES

Assess the safety and durability of combined HAPC and ESG compared to traditional ESG

Assess weight loss and improvement in obesity related co-morbidities in combined HAPC and ESG compared to ESG alone.

STUDY DESIGN

General Description

This is a single-center, randomized, single-blinded clinical trial evaluating the efficacy and safety of combined HAPC and ESG for weight loss and improvement in obesity-related co-morbidities compared to ESG alone in participants with a BMI ≥ 30 and ≤ 40 kg/m² who have failed to achieve and maintain weight loss with a non-surgical management.

Participants will be recruited from outpatient clinical weight loss clinics and from study-related institutional review board (IRB) approved advertisements.

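### The %EWL ANCOVA refers to covariates that the plan never names, so no baseline BMI term is planned although %EWL depends on BMI by construction

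*Combined protocol and SAP*

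**What the plan says.** Under Endpoints Effectiveness, the secondary endpoints include "Excess weight loss (EWL) at 6 and 12 months between both groups" and the proportion with at least 25% EWL at the same times. Footnote c to section 8.2.3 divides weight lost by pre-operative weight minus ideal weight, and sets ideal weight at BMI 25. The General Description restricts entry to "participants with a BMI ≥ 30 and ≤ 40 kg/m² who have failed to achieve and maintain weight loss".

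Section 8.2.2 places %EWL in its list of continuous outcomes, which "will be compared between treatment arms using ANCOVA with adjustment for the same variables specified in the primary analysis". The primary analysis it points to is section 8.2.1, whose whole text is "The primary outcomes are durability of plications and endoscopic sutures on repeat endoscopy at 6 months, in the two randomized arms". That sentence gives outcomes, but no model and no covariates. The Missing Data section calls the primary analysis a hierarchical regression model and lists no covariates either.

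Section 8.2.2 then assigns the ≥25% EWL proportion to a Pearson chi-square test and ends with "Among all subjects, %EWL will be compared at 6 and 12 months between both arms of the study", which names no method.

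**The concern.** The denominator of %EWL runs from 5 to 15 BMI units across eligible patients, so the same percentage of body weight lost becomes a very different %EWL depending on where the patient started. A covariate that strong belongs in the model. The plan promises adjustment, but the cross-reference leads nowhere.

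For blood pressure or HbA1c, a reader could fill the gap with the usual ANCOVA default, the baseline value of the outcome. That default does nothing for %EWL, which is zero for everyone at baseline. The starting BMI has to be named.

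At stake are the precision of a named secondary endpoint at two time points, and how far a chance difference in BMI between two groups of 12 can make the arms look different in %EWL when their %TBWL is the same. If the covariate is left open, it may also be chosen after the data are seen.

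**Working it through.** The plan gives no power, SD or effect size for %EWL, so it has no figure to reproduce.

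**1. Scaling (documents only).** Write pre-operative weight as BMI × h² and ideal weight as 25 × h². Footnotes b and c then give

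%EWL = %TBWL × BMI/(BMI − 25), and %TBWL needed for 25% EWL = 25 × (BMI − 25)/BMI.

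| BMI | Multiplier | %EWL at 15% TBWL | %EWL at 19% TBWL | %TBWL needed for 25% EWL |
|---|---|---|---|---|
| 30 | 6.00 | 90.0 | 114.0 | 4.17 |
| 35 | 3.50 | 52.5 | 66.5 | 7.14 |
| 40 | 2.67 | 40.0 | 50.7 | 9.38 |

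The 15–19% range is the Abstract's figure for ESG.

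**2. Share of %EWL variance explained by BMI (assumptions needed).** Assume TBWL has mean μ = 15–18% (the Background section's range) and SD σ = 5–10 (not in the documents), independent of BMI. Let M = BMI/(BMI − 25). Then

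Var(%EWL) = (μ² + σ²)E(M²) − μ²E(M)², and linear R² = [μ² cov(BMI, M)²/Var(BMI)] / Var(%EWL).

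- BMI uniform on 30–40: E(M) = 3.747, E(M²) = 14.826, cov = −2.465, Var(BMI) = 8.333.
  - μ = 18, σ = 5: R² = 236.3/626.6 = 0.38.
  - μ = 15, σ = 10: R² = 164.1/1660.4 = 0.10.
- BMI clustered (normal with location 36 and scale 2.5, truncated to 30–40): E(M) = 3.432, E(M²) = 12.103, cov = −1.180, Var(BMI) = 4.652.
  - μ = 18, σ = 5: R² = 96.9/407.4 = 0.24.
  - μ = 15, σ = 10: R² = 67.3/1283.1 = 0.05.

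**3. Effect on the standard error.** The gross cut is 1 − √(1 − R²). Estimating one covariate at N = 24 inflates the variance by about (N − 3)/(N − 4) = 21/20, so the net cut is 1 − √(1.05 × (1 − R²)).

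| Case | R² | Gross cut | Net cut |
|---|---|---|---|
| Uniform, μ 18, σ 5 | 0.38 | 21% | 19% |
| Uniform, μ 15, σ 10 | 0.10 | 5% | 3% |
| Clustered, μ 18, σ 5 | 0.24 | 13% | 11% |
| Clustered, μ 15, σ 10 | 0.05 | 3% | 0% |

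**4. Chance imbalance.** The SD of the between-arm difference in mean BMI is SD(BMI) × √(2/12).

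- Uniform: 2.887 × 0.408 = 1.18. A difference over 1 unit has probability 0.40, and over 2 units 0.09.
- Clustered: 2.157 × 0.408 = 0.88. The probabilities are 0.26 and 0.02.

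At mean TBWL 16%, each unit of imbalance shifts %EWL by about 16 × 2.465/8.333 = 4.7 points (uniform) or 16 × 1.180/4.652 = 4.1 points (clustered). If every patient lost exactly 15%, BMI imbalance alone would move the arm difference with an SD of 3.5 (clustered) to 5.4 (uniform) points.

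**5. Validity and power.** Simulated trials (12 per arm, 20,000 per scenario, two-sided α = 0.05 assumed) give type I error of 0.045–0.052 with or without BMI in the model. For an assumed true effect of +5 TBWL points at mean 15%, adding BMI raises power from 0.43 to 0.59 (uniform, SD 5) at best and from 0.22 to 0.23 (clustered, SD 9) at least.

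**6. The ≥25% EWL proportion.** At 15–19% TBWL, a patient at any eligible BMI clears the bar, which is at most 9.38% TBWL. BMI therefore matters only for below-average responders. With BMI uniform, mean TBWL 15% and SD 7, about 91% below BMI 35 and 83% at or above it reach 25% EWL. In the same setting, an exact test stratified at BMI 35 rejects about 2% of the time under a +5-point effect, against about 4–5% for the chi-square test. Under no effect the rates are about 1% and 2%.

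**The case against.** The best counter-argument is that the plan does adjust %EWL. Section 8.2.2 puts it under ANCOVA, and the undefined covariates affect every outcome in that list. This stands. A reader might infer that %EWL is to be compared without adjustment, or that the closing sentence of section 8.2.2 adds a second, plain test. The documents do not support either reading. That sentence names no test, its time points match the endpoint list, and section 8.2.3 makes mITT primary for all efficacy analyses. BMI is neither specified nor excluded.

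A reader might also infer that baseline BMI biases the arm comparison or determines its result. It does not. Randomization keeps the unadjusted test valid, chance imbalance is already reflected in its standard error, and BMI explains a minority of the variance in every scenario examined.

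The size also rests on assumptions. Clustering BMI near 36 shrinks the gain, to almost nothing when TBWL is very variable. Randomization is described as variable block in one place and stratified block in another, with no strata named. If BMI class is a stratum, the imbalance figures in step 4 are too high, although the precision argument remains.

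Finally, these are secondary endpoints in a pilot that disclaims a power calculation, and %TBWL, which lacks this scaling, is already listed first among them. That limits the weight of the point but does not remove it.

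**Conclusion.** The point holds as a gap in specification with a free remedy. As written, the %EWL model contains no BMI term, because the variables it borrows are not given anywhere. The scaling from 6.0 to 2.67 follows from the documents alone. The size of the benefit does not: it rests on assumed BMI and TBWL distributions, with TBWL taken as independent of BMI. Over the range shown, BMI explains about 5–38% of the variance of %EWL, and adjustment cuts the standard error by about 3–21% gross, or about 0–19% net at N = 24.

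The consequence is lost precision and weaker protection against chance imbalance, not an invalid test. For the ≥25% EWL proportion, the dependence on BMI calls for care in interpretation. It does not justify a different test.

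**What to change.** In section 8.2.2:

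- Name baseline BMI as a covariate in the %EWL ANCOVA at both 6 and 12 months, calculated from the same pre-operative weight that enters footnotes b and c.
- State that the closing sentence on %EWL refers to this same adjusted mITT analysis.
- State that the ≥25% EWL proportion will be interpreted alongside %TBWL, because the weight loss needed to reach it runs from 4.2% to 9.4% across eligible BMI. A BMI-stratified exact test is not advised, since at 12 per arm it is more conservative and gives up what little power there is.

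The cost is a few lines of SAP wording and one degree of freedom in the model. Height, weight and BMI are already collected at screening, and weight and BMI again on the procedure day. The change should be made before outcome data are examined by arm.
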